1. Confirmed COVID-19 positive test result (including presumptive positive).
2. Hospitalization
3. Requiring ≥ 4 liters/min O_2 nasal cannula to maintain oxygen saturation $\geq 92\%$, but not mechanically ventilated
4. Age ≥ 18 years old.
5. Access to a phone in the hospital room or an electronic device that is capable of receiving phone calls and/or video calls and/or e-mail.
6. Able to read/write/speak English or Spanish fluently.
7. Subjects must have the capacity to provide consent or an appropriate Legally Authorized Representative (LAR) to provide informed consent.
8. Negative pregnancy test for women of childbearing potential.

Exclusion Criteria:

1. Severe allergy to any IVIG product formulation
2. History of DVT, PE, thromboembolic stroke or other thrombotic events

3. Hypersensitivity to corn. Octagam® contains maltose which is a sugar derived from corn.
4. Uncontrolled hypertension (SBP>180 mm Hg or DBP>120mmHg)
5. Active participant in another research treatment study
6. Mechanically ventilated patient
7. Code status is Do Not Resuscitate or Do Not Intubate

Age of Subjects: ≥18 years of age

Gender of Subjects: Either male or female

Racial and Ethnic Origin: Non-specific

Vulnerable Subjects: Hospitalized subjects

Study Design: Investigator initiated, open label, multicenter, two arm, randomized study to compare the impact of adding IVIG to the Standard of Care (SOC) to the SOC without IVIG. Randomization ratio will be 1:1.

Procedures and Study Visits:

1. The PI will be notified of a COVID-19 tested positive patient via hospital generated alert.
2. The PI or designee will prescreen the patient using the inclusion and exclusion criteria.
3. PI or Sub-I will contact the study team, if the patient passes prescreening.
4. The CRC will obtain an informed consent from the subject or LAR either electronically utilizing DocuSign® or with a paper copy utilizing an impartial witness:
 - a. The research team will utilize DocuSign® for the signing of the consents in order to be compliant with the infection control measures taken place for Highly Infectious Diseases. Below are the steps of the DocuSign® procedure:

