5. A urine or blood pregnancy test will be ordered using urine or blood previously collected for routine care for subjects of childbearing potential who have passed all the other screening criteria and signed consent. If no leftover urine or blood is available, the patient will be asked to take a urine pregnancy test. If the patient already had a pregnancy test during their hospitalization, the results will be extracted from the EMR and used to determine eligibility.
6. The designated research team member will randomize the subject. The randomization will be computer generated using this website in a block of 10. (<https://www.sealedenvelope.com/simple-randomiser/v1/lists>).
7. If the subject is randomized to the “study arm”, then the Research Pharmacy will enter in the order for the IVIG and will not charge the subject. If the subject is randomized to the SOC arm, there is no additional work to be completed by the Research Pharmacy.
8. There are 3 endpoints for this study: discharge to home, receipt of mechanical ventilation, or death. Once one of these endpoints is reached, the subject’s participation in the study will end. As such, the subject may be a candidate for enrollment in another research protocol where appropriate.

Dose: IVIG (Octagam) 0.5g/kg IVPB actual body weight daily x 3 days, with premedication methylprednisolone 40 mg IV push x 1 30-50 minutes before each IVIG infusion.

- Initial infusion rate of IVIG (Octagam) will be of **0.6 mL/kg/hour**, increasing to a maximum rate of 100ml/hr, if tolerated. This is consistent with the standard of care for IVIG at Sharp HealthCare.

Procedure Classification: Aside from a urine or blood pregnancy test for subjects of childbearing potential, there are no other extra tests, imaging scans or procedures that will be performed as part of the study.

Potential Hazards and Precautions: Potential hazards to subjects are described in the “Potential Risks” section, and precautions for subjects are described in the “Protection Against Risks” section.

Research team members will take precautions to minimize exposure to COVID-19 infection by obtaining informed consent electronically, and by collecting data from routine clinical tests as opposed to conducting protocol-specific tests.

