Study Timeframe: The study time frame would be from IRB approval date to the end of the pandemic or until our sites reach 40 subjects, whatever comes first. We anticipate that at the current COVID-19 rate, it should take about 6 weeks to enroll all patients from the time of study initiation.

The end of study for each individual subject will be the date of discharge from the Sharp HealthCare hospital. The subject will not be followed if there is a transfer to a non-Sharp hospital or any sub-acute care setting (i.e., SNF, LTAC, rehabilitation center). A subject's participation will also end if the subject's goals of care have transitioned to palliation, including changing the code status to Do Not Resuscitate or Do Not Intubate of which would render the patient no longer a candidate for intubation.

Method of Subject Identification and Recruitment: The PI or Sub-I will be notified of a COVID-19 confirmed positive patient via hospital generated alert as part of the Infectious Disease Team at each hospital.

Subject Capacity: Subjects who are cognitively impaired or lack the capacity to provide informed consent (as described in HRP-013 section 5.2) may be enrolled in the study if they have an appropriate LAR to provide written informed consent on their behalf. The researchers will follow the guidance outlined in HRP-013 "Legally Authorized Representatives (Surrogate Consent)" when obtaining surrogate consent.

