Data Collection/ Assessment Instruments: The Case Report Form will include the following data elements: Demographics (age, gender, race/ethnicity, insurance), medical status (pre-existing comorbid conditions (based on the Charlson Comorbidity Index), ferritin level (results will only be collected if lab is ordered as part of the subject's standard of care), CRP level. The tool used to calculate the Charlson Comorbidity Index can be found here <https://www.mdcalc.com/charlson-comorbidity-index-cci#next-steps>). Other data to be collected from standard of care procedures includes vital signs, result of blood or urine pregnancy test, serum creatinine, calculated creatinine clearance (Cockcroft and Gault equation), white blood cell count, platelet count, maximum body temperature in the past 24 hours and oxygen demand rate, whether or not there is an admission to the ICU, any concomitant antimicrobials including azithromycin, doxycycline, hydroxychloroquine, chloroquine, and remdesivir. Receipt of interventions will include standard of care in those who have tested positive for COVID-19. Measures of healthcare service utilization will include length of stay, number of days in ICU, number of days requiring oxygenation, discharge disposition and mortality.

Data Collection Resources: The Study Coordinator will complete the Case Report Forms, with assistance from Sharp's Clinical Analytics team to extract information from the EMR.

Data Analysis: Descriptive statistics will be conducted to describe frequencies of demographics and clinical characteristics including the following: age at discharge, gender, race/ethnicity, payer, comorbid conditions based on the Charlson Comorbidity Index, receipt of medical interventions (mechanical ventilation, medications) and healthcare service utilization (ICU admission and Length of Stay in the hospital). Frequencies and descriptive statistics will be conducted using chi-square or 2-tailed Fisher exact statistics depending on the final sample size for categorical data and t-tests for continuous data. Kaplan-Meier analysis will be performed with assistance from a biostatistician regarding the endpoints of mechanical ventilation and discharge to home endpoints. We do not anticipate number of patient deaths for be sufficient for a meaningful analysis.

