Privacy of Subjects: There will be limited access to the subject due to standard of care isolation protocols. The Informed Consent process will emphasize the personal nature and privacy

concerns related to communications regarding the subject's condition and infectious disease test results.

Confidentiality of Data and Storage: Subjects information will be recorded on a master list accessible to the investigator and research staff. It will be stored electronically on a secure server. Information included on master list: subject ID, hospital, date screened, patient name/room#, FIN, group, age, gender, enrollment status, telephone number, email address, and address. All binders will be stored and secured at Sharp's Center for Research office in accordance with all regulatory and organizational requirements, and will be accessed only by authorized personnel. No subject-specific data will be reported. Sharp FIN will be used to link subject records across data systems and hospital visits. Protected Health Information (PHI) will be safeguarded as specified by Sharp HealthCare policy. There is a risk of disclosure of PHI from inappropriate access to the study database. All efforts will be made to protect PHI, including password protecting the database with access only allowed to study members who are Sharp HealthCare employees. All datasets will be de-identified prior to any statistical analyses conducted by the Statistician. Identifiers will be destroyed two years after study end date, once data has been aggregated for reporting.

Data Monitoring: A designated person (or group of designees) who is not part of the Research Team will review and will report the outcomes to the SHC IRB after a total of 10, 20, and 40 patients (5, 10, and 20 in each arm, respectively) have completed/met the endpoint of the study. Additionally, if unexpected adverse outcomes are identified at any point in the enrollment the designated person will review the case on an individual basis.

Benefits to Individual Subjects: Potential reduction in ICU hospitalization, potential avoidance of mechanical ventilation and potential decrease in length of stay in the hospital.

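### The list is blocked by count only and the ventilation comparison is unadjusted, although oxygen requirement is known at entry: this costs precision and credibility, not validity

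*Combined protocol and SAP*

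**What the plan says.** Study Design sets the allocation: "Randomization ratio will be 1:1". Procedures and Study Visits, item 6, gives the method: "The randomization will be computer generated using this website in a block of 10". The text available for review names no stratification factor.

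Study Timeframe runs enrolment to the end of the pandemic or "until our sites reach 40 subjects, whatever comes first". Data Monitoring places outcome reviews at 10, 20 and 40 patients, which it breaks down as "5, 10, and 20 in each arm, respectively".

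Inclusion criterion 3 admits patients "Requiring ≥ 4 liters/min O_2 nasal cannula to maintain oxygen saturation" at the stated level, "but not mechanically ventilated". It states no upper flow limit. Data Collection/Assessment Instruments lists "oxygen demand rate" among the values taken from routine care.

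Data Analysis plans chi-square or Fisher tests for categorical data, t-tests for continuous data, and Kaplan-Meier analysis for ventilation and discharge home. It mentions no covariate or stratum.

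**The concern.** The primary objective is progression to mechanical ventilation. Oxygen requirement at entry is a natural candidate predictor of that event, although the documents do not quantify the relation. It is known before allocation because eligibility depends on it. Blocks of 10 equalize the number of patients per arm and do nothing to equalize their severity. With 20 per arm, four patients make 20 percentage points, so a visible difference in starting severity can easily arise by chance.

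The plan has no second line of defence, because the analysis is unadjusted as well. At stake are some precision in the ventilation comparison and the credibility of a small open-label trial if its baseline table shows one arm sicker than the other.

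**Working it through.** **Inputs from the documents.** 40 patients at 1:1, so 20 per arm and four full blocks of 10. The plan states no imbalance probability, target effect, power or alpha, so there is no figure of its own to reproduce.

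**Assumptions.** A two-level oxygen factor with a share *p* of patients in the higher group, and ventilation risks by group of 60% and 20% (strong gradient) or 50% and 30% (weak gradient). None of these is in the documents.

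**Step 1: chance imbalance.** If patients' severities are independent, the numbers of higher-oxygen patients in the two arms are independent Binomial(20, *p*) counts, with or without blocking by count. The exact probability that they differ by at least 4 patients (20 points), in either direction, is:

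| Share *p* | P(at least 20 points) |
|---|---|
| 10% | 6.3% |
| 20% | 16.4% |
| 30% (or 70%) | 22.6% |
| 40% | 25.8% |
| 50% | 26.8% (maximum) |

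At *p* = 50% the standard deviation (SD) of the imbalance is √(2 × 0.5 × 0.5 / 20) = 0.158, or 15.8 points. An imbalance of at least 30 points has probability 8%. An imbalance of at least 20 points in one given direction has half the tabled probability, 13.4% at *p* = 50%.

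**Step 2: effect on the risk difference.** Shift = imbalance × risk gradient.
- Strong gradient: 0.20 × (0.60 − 0.20) = 0.08.
- Weak gradient: 0.20 × (0.50 − 0.30) = 0.04.

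At *p* = 50% the overall risk is 40% under either gradient. With no treatment effect, the standard error of the raw risk difference is √(2 × 0.4 × 0.6 / 20) = √0.024 = 0.155. The shifts are therefore 0.08/0.155 = 0.52 and 0.04/0.155 = 0.26 standard errors.

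**Step 3: variance that can be removed (*p* = 50%).** With perfect balance on the factor, only the within-group variance remains.
- Strong gradient: the mean of 0.6 × 0.4 and 0.2 × 0.8 is 0.20. The variance is 2 × 0.20/20 = 0.020 against 0.024, a fall of 17% at most.
- Weak gradient: the mean of 0.5 × 0.5 and 0.3 × 0.7 is 0.23. The variance is 0.023 against 0.024, a fall of 4% at most.

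Simulations of 20,000 to 40,000 trials agree, within simulation error. Under the strong gradient the SD of the risk difference was:

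| Design and analysis | SD | Fall in variance |
|---|---|---|
| Blocks of 10, unadjusted | 0.154 to 0.155 | reference |
| Blocks of 10, analysis stratified by oxygen group | 0.142 to 0.144 | about 14% to 15% |
| Two oxygen lists, random blocks of 4 and 6 | 0.142 to 0.143 | about 14% to 16% |

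A 15% fall is worth 1/0.85 − 1 = 18% more patients, about 7 of 40. Under the weak gradient the simulated fall was about 2% to 5%.

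**Step 4: what stratified lists do to balance.** At *p* = 50%, two lists with blocks of 4 and 6 cut the SD of the imbalance from 15.8 to about 3.7 points, and no simulated trial reached 20 points. Total arm sizes differ by about 1 patient on average. Arms are exactly equal in about 55% of trials at each of 10, 20 and 40 randomized.

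**The case against.** Three stronger readings are tempting, and the documents do not support them.

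- **The trial is biased or its test invalid.** Unstratified 1:1 blocked randomization is valid. Chance imbalance is already covered by the type I error of the chi-square or Fisher test.
- **One such trial in four starts badly imbalanced, whatever the case mix.** That figure needs a share of about 30% to 70%. The documents give neither a cut nor a share, and 26.8% is the maximum of the calculation. The entry criterion refers to nasal cannula, so the spread of oxygen need at entry is unknown.
- **Imbalance could create or hide an effect as large as the one sought.** The available text states no effect sought. The shift of 8 points also compares poorly with what the test can detect: with 8 of 20 events in one arm, two-sided Fisher first falls below 0.05 at 1 of 20 in the other (p = 0.020; 2 of 20 gives p = 0.065). That is a 35-point difference.

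A fourth objection largely stands: most of the precision can be had without touching the list. A stratified analysis alone cuts the variance by about 14% to 15%, against about 14% to 16% for stratified lists. A fifth also stands: blocks of 10 match the per-arm counts in Data Monitoring, and stratified lists would often break that match. The present match is itself only approximate, since reviews are triggered by patients completing and not by randomization.

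What survives is that the plan takes neither route. It has no stratified list and no pre-specified adjustment, for a factor it already records. If the cut is set to divide eligible patients about evenly, a share near 50% follows from the design and is no longer a guess about case mix.

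**Conclusion.** The point holds as a worthwhile improvement and is not an error in the trial's validity. Blocking by count combined with an unadjusted ventilation comparison leaves avoidable noise. For an assumed share of 30% to 70%, about 23% to 27% of trials would show an imbalance of at least 20 points in one direction or the other; for smaller shares this falls to 16% (20% share) or 6% (10% share).

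The gain from acting depends on how strongly oxygen requirement predicts ventilation, which the documents do not say. It is about 15% of the variance at 60% against 20%, and small (about 2% to 5%) at 50% against 30%. Beyond precision, the benefit is a baseline table that does not invite doubt about the comparison.

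**What to change.** 1. **Analysis (the main change).** State in Data Analysis that the ventilation comparison is stratified by, or adjusted for, oxygen requirement at randomization, for example with a Mantel-Haenszel risk difference over two oxygen groups. Fix the cut before any outcome is seen. This gives most of the gain at essentially no cost. It needs the oxygen value at randomization to be recorded as such, because "maximum body temperature in the past 24 hours and oxygen demand rate" does not say which time point the oxygen value refers to.

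2. **Allocation (if the list can still be regenerated before enrolment).** Use two lists on that one pre-set cut, chosen so that about half of current eligible patients fall on each side, with small blocks of varying size. Do not add site as a further stratum at 40 patients.

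3. **Data Monitoring.** If the lists are stratified, reword the review counts of 5, 10 and 20 per arm as approximate.

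The cost is a second list, one time-stamped value per patient, and arms that may end slightly unequal (about 1 patient on average).

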Subject/Representative Comprehension: Subjects/LARs must have the ability to understand the requirements of the study, provide informed consent, and provide authorization of use and disclosure of personal health information. Subjects with impaired cognitive or decision-making capacity (determined by the PI or designee's assessment of the subject's ability to understand and express a reasoned choice, according to HRP-013 section 5.2.1) must have an appropriate LAR to provide consent on their behalf. If the research subject lacks capacity to consent, the investigator will describe the research to the subject in a manner consistent with the standard consent process and indicate the intent to obtain surrogate consent. This communication will be documented in the research record. If the research subject is non-responsive, the investigator will document this observation in the research record and a note in the subject's medical record that references the research record. If the research subject expresses resistance or dissent to being in the research or to the use of the surrogate consent by word or gesture, she/he will be excluded from the research study.

Documentation of Consent/Assent: Consenting will be conducted as described above in the Procedures and Study Visits section. Consents will be printed and stored in the subject's research binder in a secure location.

Reimbursements or Payments: None

Costs to the Subject: None

Data Sources: Sharp HealthCare electronic medical records (EMR) for hospital in-patients who meet inclusion criteria at acute care facilities.

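### Two different end-of-participation rules leave the data cut-off for ventilated patients undefined; if the earlier one is applied, hospital days after intubation are lost and a true IVIG benefit on total hospital days is shrunk or reversed

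*Combined protocol and SAP*

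**What the plan says.** Four places in the combined protocol and SAP bear on when a ventilated patient's data stop.

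- **Procedures and Study Visits, item 8.** The endpoints are discharge home, ventilation and death. "Once one of these endpoints is reached, the subject’s participation in the study will end". The next sentence draws one consequence: "As such, the subject may be a candidate for enrollment in another research protocol where appropriate".
- **Study Timeframe.** "The end of study for each individual subject will be the date of discharge from the Sharp HealthCare hospital". Two earlier exits are given. One is transfer: "The subject will not be followed if there is a transfer to a non-Sharp hospital or any sub-acute care setting". The other is a move to palliation or to a code status that rules out intubation. Ventilation is not mentioned.
- **Termination of the Study, items 1 to 3.** Item 1 keeps data collection going to discharge for a subject who stops study treatment early. Items 2 and 3 concern IVIG dosing at ventilation or ICU entry and are silent on data.
- **Data Sources and Data Collection.** The source is "Sharp HealthCare electronic medical records (EMR) for hospital in-patients". The utilisation measures are "length of stay, number of days in ICU, number of days requiring oxygenation, discharge disposition and mortality", with no cut-off at intubation.

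The two secondary objectives are days on oxygen and total hospital days. Data Analysis assigns "t-tests for continuous data".

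**The concern.** A patient who is intubated and stays in a Sharp hospital has met item 8's rule but not the Study Timeframe rule. A coordinator could reasonably close the case report form at intubation. Study Timeframe moves from end of study to participation as if they were the same event, and Data Monitoring groups patients who have completed the study with those who have met an endpoint.

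Termination item 1 does not settle the matter. Control patients have no study treatment to stop. IVIG patients intubated after finishing the course ("0.5g/kg IVPB actual body weight daily x 3 days") have not stopped anything early.

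At stake is the comparison of hospital days. A stay cut at intubation looks short although the patient did badly. If IVIG prevents intubation, as the trial hypothesises, more days are removed from the control arm, and the effect being sought erodes its own secondary result. Oxygen days suffer in the same way if ventilated days count as oxygen days, which the plan does not say.

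**Working it through.** The available text gives no expected ventilation risk, mean stay or SD, so there is no planned figure to reproduce. The check asks what follows if item 8 sets the data cut-off.

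**Inputs**
- 20 per arm: 40 subjects (Study Timeframe), allocated 1:1 (Study Design).
- D = 14 days after intubation. The Background says that ventilated patients frequently need two weeks of support. This stands in for the whole stay after intubation.
- T = 9 days to ventilation, the Background average from hypoxia. Patients are already hypoxic at entry, so T = 3 and T = 5 were also tried (assumed).
- L = stay if never ventilated, assumed 7, 10 or 14 days.
- p = risk of ventilation in each arm, assumed.

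**Formulas**
- Mean days with full follow-up: p(T + D) + (1 − p)L
- Mean days if cut at intubation: pT + (1 − p)L
- Days lost per randomised patient: pD
- Shift against IVIG: p_SOC × D_SOC − p_IVIG × D_IVIG, which is D(p_SOC − p_IVIG) when D is the same in both arms.

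**Size of the shift, D = 14 in both arms**

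| p_SOC vs p_IVIG | Shift (days) |
|---|---|
| 50% vs 25% | 14 × 0.25 = 3.5 |
| 40% vs 20% | 14 × 0.20 = 2.8 |
| 1/3 vs 1/6 | 14 × 1/6 = 2.3 |
| equal risks | 0 |

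In the first row, 20 × 0.50 × 14 = 140 patient-days are lost on control and 20 × 0.25 × 14 = 70 on IVIG. If half of ventilated patients die halfway through support (assumed), D = 0.5 × 14 + 0.5 × 7 = 10.5, and the shifts in the first three rows become 2.6, 2.1 and 1.75 days.

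**Shrunk or reversed?** If IVIG acts only by preventing ventilation, the true benefit is (p_SOC − p_IVIG)(T + D − L), and the benefit seen after the cut is (p_SOC − p_IVIG)(T − L). The second is negative whenever T is below L. With T = 9, D = 14, L = 10 at 50% vs 25%:
- Full follow-up: control 0.5 × 23 + 0.5 × 10 = 16.5; IVIG 0.25 × 23 + 0.75 × 10 = 13.25; benefit 3.25 days.
- Cut at intubation: control 0.5 × 9 + 0.5 × 10 = 9.5; IVIG 0.25 × 9 + 0.75 × 10 = 9.75; apparent benefit −0.25 days.

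At 1/3 vs 1/6, the same inputs turn 2.17 into −0.17. Over T = 3, 5, 9 and L = 7, 10, 14 at these two pairs of risks, true benefits of 0.50 to 4.00 days become −2.75 to +0.50, with the sign reversed except at T = 9, L = 7. If IVIG also shortens the stay of never-ventilated patients by 2 days (T = 3 or 9), 2.17 to 5.50 becomes −1.25 to +2.00, so reversal is possible but not inevitable.

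**When the direction turns.** The shift favours IVIG only if p_IVIG × D_IVIG exceeds p_SOC × D_SOC. With D_SOC = 14, D_IVIG must exceed 0.5 × 14 / 0.25 = 28 days when IVIG halves ventilation, or 0.4 × 14 / 0.3 = 18.7 days at 40% vs 30%.

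**Scale.** For an assumed SD of 8 to 12 days, the standard error of the difference is SD × √(2/20), or 2.5 to 3.8 days. A 3.5-day shift is then about 0.9 to 1.4 standard errors.

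**The case against.** The strongest reply is that full-stay collection is the better-supported reading. Item 8 speaks of participation, never says that data collection stops, and goes on only to release the patient for another protocol. Study Timeframe puts the end of study at discharge. ICU days, disposition and mortality would be largely uninformative for ventilated patients if collection stopped at intubation, and the days stay retrievable from the hospital record. All of this stands. A reader might infer that the plan definitely discards days after intubation; the documents do not support that. What remains is that no sentence states the rule.

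A reader might also infer an unequal cut-off, with ventilated IVIG patients followed to discharge under Termination item 1 and ventilated control patients dropped under item 8. That would bias against IVIG even with no treatment effect. It requires item 1 to override item 8 for IVIG patients only, and protocol-driven stops to count as a subject stopping early. No text says either. The documents also give no share of IVIG patients who would be intubated during the three-day course, so no size is claimed for this reading.

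It is fair, too, that the direction depends on stay after intubation being similar in the two arms, that every ventilation risk used here is assumed, and that only secondary objectives are touched.

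**Conclusion.** The point holds as a conflict between two stated rules, with a conditional consequence. Item 8 and Study Timeframe end a ventilated patient's participation at different times, and nothing fixes one data cut-off for both arms. Full-stay collection is the likelier intent.

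If item 8 were applied to data, a true benefit on total hospital days would be understated by roughly 2.3 to 3.5 days under the assumed halvings of ventilation risk, or 1.75 to 2.6 days with shorter stays after intubation because of deaths. The apparent effect could change sign. With equal risks and equal stay after intubation there is no shift. The direction turns only if stay after intubation is much longer on IVIG.

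The primary ventilation endpoint is unaffected. With 20 per arm, settling the rule protects the estimate more than it changes a test result. Severity is minor.

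**What to change.** Reconcile Procedures item 8, Study Timeframe and Termination of the Study with one data rule for both arms, before any extraction:

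- Reaching an endpoint, stopping IVIG, a change to palliation or code status, or joining another study does not end outcome data collection. Medical-record data are collected for every randomised patient to Sharp discharge or in-hospital death. This deliberately changes the Study Timeframe exit for palliation, for data only; the clinical stopping text is left as it is.
- Say that item 8 concerns release for co-enrolment, if that is the intent.
- State whether ventilated days count as oxygen days.
- Flag later co-enrolment by arm and report transfers by arm with disposition, since transferred patients are not followed. Keep all randomised patients in the main day comparison. Leaving out those co-enrolled after intubation would select on an event that treatment may influence.

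No change of test is needed. Ranking death as the worst outcome would alter what the day comparison estimates and is a separate decision.

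The cost is a wording amendment, possibly a consent line (the consent pages were not available to check), and a longer record extract, with no added visits, tests or patients. One drawback remains: days after co-enrolment may partly reflect another trial's treatment.
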